5.5.2.3 All Early Withdrawal Subjects

For any subject who early terminates from the study (including subjects who withdraw their consent), survival information may be ascertained via public database search at the end of the study.

6. STUDY TREATMENTS

6.1 Treatment Blinding

The Run-in Phase is single-blinded for the subject.

To minimize the potential for bias during the Treatment Phase, treatment randomization information will be kept confidential by an unblinded biostatistician and will not be released to the Investigator or Investigator site personnel until the study database has been locked. The blind will be maintained for subjects, site personnel, Sponsor and vendor staff, except for unblinded staff required for the development of the final randomization schedule and for production of unblinded materials for the Data and Safety Monitoring Board (DSMB) and Sponsor's Drug Safety staff in situations where unblinding is necessary to comply with regulatory requirements.

Clinical Trial Supply Management will have access to overall patiromer/placebo usage for management of patiromer/placebo packaging and distribution activities and oversight of patiromer/placebo stock levels at drug depots and study sites.

If the Investigator or site study staff becomes aware of a subject's study treatment assignment, efforts should be made to not disclose treatment assignments to other study staff, subjects, or their caregivers. Blinded Sponsor staff will also remain blinded to treatment assignment.

The Investigational Pharmacist or the qualified designee as assigned by the Principal Investigator will exclusively be responsible for investigational medicinal product (IMP) handling and should not be involved in any other study procedures (see Section 6.5 for more details).

Subjects will be instructed to refrain from discussion of their study drugs with the site staff (except with the Investigational Pharmacist or the qualified designee as assigned by the Principal Investigator) or other subjects, and that any questions regarding the study drug should be directed to the Investigational Pharmacist or the qualified designee as assigned by the Principal Investigator only.

6.1.1 Unblinding

In the case of a medical emergency, the Investigator may request that the blind be broken if it is considered important to the management of the medical emergency. In such cases, the Investigator will be unblinded via the interactive web response system (IWRS). The Investigator should make every reasonable attempt to notify study Medical Monitor before breaking the blind. The Investigator may inform the subject and/or his/her treating physician of the treatment assignment.

Other situations where unblinding may be necessary are for study-specific suspected unexpected serious adverse reaction (SUSAR) and aggregate safety reporting to health

authorities. In these cases, Sponsor's Drug Safety personnel must know the subject's treatment allocation to ensure compliance with reporting requirements.

6.2 Dosage Forms/Formulation

6.2.1 Patiromer for Oral Suspension (Patiromer) or Placebo (Microcrystalline Cellulose)

Patiromer or placebo (microcrystalline cellulose) will be provided to the subject blinded, as a powder for oral suspension in packets.

Information on patiromer is provided below:

Active Ingredient: Patiromer sorbitex calcium

Chemical Name: Calcium, hydrolyzed divinylbenzene-Me 2-fluoro-2-propenoate-1,7-octadiene polymer sorbitol complexes

Generic Name: Patiromer sorbitex calcium, powder for oral suspension

Trade Name: Veltassa

Strength: Each packet contains 8.4 g patiromer

Excipients: Xanthan gum

Dosage Form: Powder for oral suspension

Manufacturer: Patheon Inc. or OM Pharma S.A.

Labeling: Almac or Catalent

Storage: 2–8°C (see the Pharmacy Manual for additional details)

All IMPs used in this study have been manufactured in accordance with current Good Manufacturing Practice.

6.3 Drug Dosage and Administration

6.3.1 Treatment Arms

All enrolled subjects will be treated with patiromer single-blinded during the Run-in Phase. After the Run-in Phase, eligible subjects will be randomized in a 1:1 ratio to treatment with patiromer or placebo in a double-blinded fashion.

6.3.2 Dosing and Administration Guidelines

6.3.2.1 Patiromer/Placebo

The starting dose will be 1 packet/day and may be taken either with food or without food. Based upon the K⁺ management algorithms (Section 6.7.1.1 and Section 6.7.1.2),

patiromer/placebo may be increased by 1 packet per day in intervals of at least 1 week (± 3 days). For subjects who become hypokalemic ($K^+ < 4.0$ mEq/L), patiromer/placebo must be decreased to a minimum of 0 packets/day (see Section 6.7.1.1). If serum K^+ increases from $< 4.0 - \geq 4.0$ mEq/L and remains between $\geq 4.0 - \leq 5.0$ mEq/L, patiromer/placebo must not be resumed yet. Resume patiromer/placebo only when $K^+ > 5.0$ mEq/L to prevent re-inducing or aggravating hypokalemia. Doses of patiromer/placebo will be 0 packets/day, 1 packet/day, 2 packets/day, and 3 packets/day (maximum dose).

Patiromer/placebo are for oral administration only. Each dose must be prepared immediately prior to administration. Patiromer/placebo should be taken at least 3 hours before or 3 hours after administration of other orally administered medications. Patiromer/placebo should be taken once daily, and preferably at the same time of day, consistently. An accidentally missed dose can be taken later on the same day but shall not be taken the next day. At the discretion of the Investigator, the following drugs may be co-administered with patiromer/placebo: allopurinol, amlodipine, amoxicillin, apixaban, aspirin, atorvastatin, cephalexin, cinacalcet, clopidogrel, digoxin, furosemide, glipizide, lisinopril, lithium, metoprolol, phenytoin, rivaroxaban, spironolactone, trimethoprim, valsartan, verapamil, and warfarin (see the Investigator's Brochure (IB), Version 13.0, dated 15 July 2020, for additional information [30]).

Patiromer/placebo suspension must not be heated (e.g., microwaved) or added to heated foods or liquids. Patiromer/placebo must not be taken in its dry form but must be mixed with water, apple, or cranberry juice only. Prepare patiromer/placebo doses following the steps below:

- Measure 1/3 cup (approximately 80 mL) of water. Pour half of the water into a glass, then add the contents of the prescribed number of patiromer/placebo packets and stir. Add the remaining half of the water and stir thoroughly. The powder will not dissolve, and the mixture will look cloudy. Add more water to the mixture as needed for desired consistency
- Drink the mixture immediately. If powder remains in the glass after drinking, add more water, stir, and drink immediately. Repeat as needed to ensure the entire dose is administered

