- If local serum K⁺ is ≥4.3-≤5.0 mEq/L at the first week during the Run-in Phase, patiromer must be started at 1 packet/day
- If local serum K⁺ is ≥4.0-≤4.3 mEq/L at the first week during the Run-in Phase, patiromer may be started at 1 packet/day; initiation or increase of patiromer dose should be made with caution when local serum K⁺ is ≥4.0-≤4.3 mEq/L to avoid inducing hypokalemia

- If local serum K^+ decreases from >4.3 mEq/L to values <4.3 mEq/L, remaining ≥ 4.0 mEq/L, patiromer may be down-titrated by 1 packet/day (minimum dose is 0 packets/day); in case of a reversal of this decrease from <4.3 mEq/L but remaining ≥ 4.0 mEq/L to values ≥ 4.3 mEq/L at following visits, patiromer may be up-titrated by 1 packet/day; subjects must receive at least 1 packet/day at serum $K^+ \geq 4.3 - \leq 5.0$ mEq/L
 - If 1 week after reducing patiromer to 0 packets/day local serum K^+ remains stable $\geq 4.0 - \leq 4.3$ mEq/L, optimize RAASi dose and resume patiromer at 1 packet/day before considering these subjects as Run-in failed; initiation or increase of patiromer dose should be made with caution when local serum K^+ is $\geq 4.0 - \leq 4.3$ mEq/L to avoid inducing hypokalemia
- If local serum K^+ is <4.0 mEq/L, patiromer must be down-titrated to 0 g/day (i.e., 0 packets/day), with confirmation of hypokalemia within 3 days and follow-up in at least (\geq) 1-week intervals until serum K^+ is ≥ 4.0 mEq/L. Resume patiromer only when local serum K^+ rises to >5.0 mEq/L
 - If 2 weeks after taking the minimum 0 packets/day, local serum K^+ remains <4.0 mEq/L during the Run-in Phase, then subject is Run-in failed

Once a subject meets all randomization criteria (see Section 5.4), they may be randomized into the Treatment Phase (double-blinded).

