6.7.1.2 Management of Serum K^+ in the Treatment Phase (Double-Blinded)

After the Run-in Phase (single-blinded), eligible subjects will be randomized in a 1:1 ratio, to treatment with patiromer or placebo (double-blinded); see Study Schema.

Randomized subjects will begin their assigned treatment (patiromer or placebo), double-blinded, using the same number of packets established for patiromer at the end of the Run-in Phase and will continue the ACEi/ARB/ARNi and MRA regimen being administered at the end of the Run-in Phase.

For subjects who are on less than the target dose of either ACEi/ARB/ARNi or MRA, up-titration should continue if serum K^+ remains in the normokalemic range (serum $K^+ \geq 4.0 - \leq 5.0$ mEq/L).

After randomization, serum K^+ will be measured prior to initiation of assigned patiromer/placebo, double-blinded, on Treatment Day 1/Baseline, and at each subsequent visit during the Treatment Phase.

The Investigator may initiate an unscheduled visit at their discretion throughout the Treatment Phase.

Protocol allowed interventions for the management of hyperkalemia during the Treatment Phase include the following:

1. Up-titration of patiromer/placebo if on <3 packets per day
2. Down-titration or discontinuation of ACEi, ARB, ARNi and/or MRA
3. Initiate or increase diuretics
4. Dietary K⁺ restriction

If local K⁺ is >5.5 mEq/L, one or more of these interventions must be initiated either individually or in combination following the recommendations by practice guidelines. Repeat the K⁺ measurement within 7 days; if local K⁺ remains >5.5 mEq/L consider repeating the intervention or using other interventions in the order described above.

If local K⁺ is between >5.0 mEq/L and ≤5.5 mEq/L, one or more of these interventions may be initiated per Investigator discretion.

Urgent treatment of hyperkalemia is in accordance with usual care and the Investigator's judgment. As described in Section 6.8.4.1, the only K⁺ binding medications permitted for use during the study are temporary use of sodium or calcium polystyrene sulfonate and sodium zirconium cyclosilicate for up to 7 days or until serum K⁺ is <5.0 mEq/L, or whichever occurs first. Patiromer/placebo must be withheld during temporary use of permitted K⁺ binding medications.

If hypokalemia develops during the Treatment Phase, study drug should be down-titrated (lowest acceptable dose is 0 packets/day) until local serum K⁺ ≥4.0 mEq/L.

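### After K+ falls below 4.0 mEq/L in the Treatment Phase, the protocol's sections do not agree on how far to reduce study drug or when to restart it

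*Protocol*

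**What the plan says.** Section 6.3.2.1 is written for patiromer and placebo together and refers to both K+ algorithms (6.7.1.1 and 6.7.1.2). For a subject with K+ below 4.0 mEq/L it says "patiromer/placebo must be decreased to a minimum of 0 packets/day", with a pointer to 6.7.1.1. Once K+ has recovered into 4.0 to 5.0, "patiromer/placebo must not be resumed yet". Restart is allowed only above 5.0, and the stated reason is to avoid bringing hypokalemia back.

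Section 6.7.1.1, the Run-in algorithm, says at the same threshold that "patiromer must be down-titrated to 0 g/day (i.e., 0 packets/day), with confirmation of hypokalemia within 3 days". Its restart sentence, beginning "Resume patiromer only when local serum", also sets the level at above 5.0.

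Section 6.7.1.2, the Treatment Phase algorithm, says for hypokalemia that "study drug should be down-titrated (lowest acceptable dose is 0 packets/day) until local serum K⁺ ≥4.0 mEq/L". The Synopsis and Section 4.1 give the same instruction. Section 6.7.1.2 then closes with a line sending re-initiation after a temporary interruption to 6.7.1.1. The hypokalemia text in the Synopsis and in 4.1 has no such line.

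**The concern.** A Treatment Phase subject whose K+ drops below 4.0 falls under both sets of text. They differ on how far the dose comes down and on the K+ level that ends the reduction. Two sites could each follow a section of the protocol and have similar subjects on different numbers of packets.

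The situation is not remote. Section 5.4 allows randomization with K+ as low as 4.0 on at least 1 packet/day, so a subject can start at the threshold. The protocol also treats it as a safety matter: Section 2 justifies the 4.0 lower limit by mortality at low-normal K+, and 6.3.2.1 justifies its restart rule by the risk of renewed hypokalemia.

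Three things are at stake:

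- whether dosing after a low K+ is consistent across sites;
- how hypokalemia is handled;
- how the dosing is reported. SAP 2.7 counts titrations and non-zero dose days, and SAP 2.4 summarizes protocol deviations. The same packet count could comply with one section and deviate from another.

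**Working it through.** This is a comparison of texts. The one related figure in the plan, 410 per arm, does not depend on this rule and is not in dispute. With a difference of 0.116, SD 0.5, two-sided 5% alpha and 90% power, 2 × (0.5 × (1.95996 + 1.28155) / 0.116)² = 390.44 per arm, and 390.44 × 1.05 = 409.96, or 410.

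**Step 1. The instructions side by side, for K+ below 4.0 in the Treatment Phase.**

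| Place in Protocol | Force | How far down | K+ that ends it | Restart pointer |
|---|---|---|---|---|
| 6.3.2.1 | must | to a minimum of 0, citing 6.7.1.1 (which mandates 0) | above 5.0 | states its own rule |
| 6.7.1.2 | should | a reduction; 0 is the floor | at least 4.0 | yes, to 6.7.1.1, after an interruption |
| 4.1 | should | a reduction; 0 is the floor | at least 4.0 | none |
| Synopsis | should | a reduction; 0 is the floor | at least 4.0 | none |

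**Step 2. The reduction, by starting dose.** Doses run from 0 to 3 packets/day.

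- On 1 packet: the only lower dose is 0, so both texts give 0.
- On 2 packets: 6.3.2.1 read with 6.7.1.1 gives 0; the other three places allow 1 or 0.
- On 3 packets: 6.3.2.1 read with 6.7.1.1 gives 0; the other three allow 2, 1 or 0.

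The texts part on the size of the reduction only for subjects on 2 or 3 packets.

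**Step 3. K+ then recovers to, say, 4.5.**

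- Subject at 0, site reading 6.7.1.2 to its end: the pointer leads to 6.7.1.1, whose bullet for K+ below 4.0 sets restart above 5.0. This agrees with 6.3.2.1, so there is no conflict.
- Subject at 0, site working from the Synopsis or 4.1: the stated end point of 4.0 has been passed and nothing there says that restart waits for more than 5.0. Section 6.3.2.1 forbids restart.
- Subject reduced from 3 or 2 packets to a non-zero dose: dosing was not interrupted, so the pointer does not apply. None of the three Treatment Phase texts says whether the subject stays at the reduced dose or returns to the former one once K+ reaches 4.0. Under 6.3.2.1 with 6.7.1.1 this subject would be at 0 and would remain there.

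**Step 4. Size.** To turn this into an effect on mean K+ one would need the share of the active arm that falls below 4.0, their packet counts, the time spent at 4.0 to 5.0 on different doses, and the K+ difference per packet. The documents give none of these.

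**The case against.** The strongest reply is that most of the conflict disappears on a careful reading.

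- **Restart.** The text in 6.7.1.2 can be read as saying when down-titration stops, not when drug is resumed, and its last line supplies the restart rule. This stands for interrupted subjects at sites that read the whole section. The Synopsis row on study treatments also refers to 6.7.1.2 for titration in general, so some readers of the Synopsis will get there. It does not help a subject left on a non-zero dose.
- **Different phases.** The Synopsis says that K+ is managed differently in the Run-in and Treatment Phases, so a mandatory 0 in 6.7.1.1 need not contradict a down-titration in 6.7.1.2. That is fair for those two sections alone. It does not dispose of 6.3.2.1, which names patiromer/placebo and brings 6.7.1.1 in by reference.
- **Wording of 6.3.2.1.** A decrease to a minimum of 0 could be read as naming a floor. The phrase is ambiguous, but the section it cites is not: "patiromer must be down-titrated to 0 g/day (i.e., 0 packets/day".
- **Timing.** Protocol version 4.0 is dated 23 June 2021. SAP 2.2 says sites were told of closure on 24 June 2021 and censors efficacy data after that date. A correction to this version could not change the exposure behind the primary analysis. This stands.

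A reader might also infer that 6.7.1.1 contradicts itself, because it says "subjects must receive at least 1 packet/day at serum" K+ of 4.3 to 5.0. That clause sits in the bullet for K+ that drops below 4.3 but stays at or above 4.0. Subjects below 4.0 have their own bullet with their own restart level. For the same reason the documents do not support a claim that the conflict decides who can be randomized: in the Run-in, 6.3.2.1 and 6.7.1.1 agree.

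**Conclusion.** The protocol contains a specific, limited inconsistency in a safety-relevant Treatment Phase dosing rule. It concerns two points: a reduction to 0 packets versus a reduction with 0 as the floor, and an end point of K+ above 5.0 versus at least 4.0. It bears mainly on subjects taking 2 or 3 packets/day and on sites that work from the Synopsis or 4.1. The consequences are uneven dosing, uneven handling of hypokalemia, and uncertainty over which doses are deviations. Under Protocol 16.1 the deviation criteria are in the Study Manual, which was not available here; it may settle that last point.

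Three stronger conclusions are tempting, and the documents support none of them:

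- That every subject with K+ below 4.0 is affected. A subject on 1 packet goes to 0 under any reading, and the restart pointer covers that subject if the site follows 6.7.1.2 to the end.
- That active-arm K+ shifts by some stated fraction of the planned 0.116 difference. Any such figure would rest on invented inputs.
- That the primary test is biased toward a false positive. The same instructions apply blind to both arms. Uneven exposure could vary or dilute the patiromer effect, but it does not inflate type I error.

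**What to change.** Reconcile the Synopsis and Sections 4.1, 6.3.2.1, 6.7.1.1 and 6.7.1.2 (including its closing restart line) into one Treatment Phase instruction for reducing and restarting study drug after K+ below 4.0. The instruction should state whether the reduction is always to 0. It should give the K+ level at which study drug may be restarted, and say what happens to a subject reduced to a non-zero dose once K+ recovers. Carry the same restart cross-reference into the Synopsis and 4.1. Which rule to adopt is for the sponsor and its clinical advisers; this point takes no view.

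The cost is protocol wording and a notice to sites, with no new procedures or data. Because sites were told of closure the day after version 4.0 was dated, the practical value now lies mostly in reporting: record which instruction is used when dosing after a low K+ is classified as compliant or deviating, and apply it the same way in both arms.

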6.4 Package and Labeling

Patiromer powder for oral suspension or placebo will be provided by the Sponsor in a blinded manner as kits labeled for clinical trial use only. Each Run-in kit contains packets of patiromer, and these kits are only dispensed during the Run-in Phase (single-blinded for the subject). Each Treatment kit contains packets of either patiromer or placebo, and these kits are only dispensed during the Treatment Phase (double-blinded). Additional details are provided in the Pharmacy Manual.

All packaging and labeling will be performed according to Good Manufacturing Practice guidelines. The study drug will be labeled in accordance with local regulations for investigational products.

6.5 Study Treatment Allocation

Each eligible subject will be assigned (blinded) to 1 of the 2 treatment groups via IWRS:

- Patiromer
- Placebo

Upon enrollment into the Run-in Phase of the study, each subject will be provided with instructions on proper dosing of patiromer and individualized instructions on when to take patiromer and other concomitant medications after considering the subject's current medication regimen, patiromer instructions regarding administration, and subject preference; see Section 7.1. The subject will be instructed to follow the agreed dosing instructions for the remainder of the study to encourage compliance. The Investigator will determine if the study drug dosing instruction requires changes at each visit and any changes will be communicated to the subject.

For subjects who qualify for the Blinded Treatment Phase, subjects will be randomized to either patiromer or placebo on Day 1/Baseline via IWRS. The study drug will be dispensed to subjects by the Investigational Pharmacist, or the qualified designee as assigned by the Principal Investigator.

Subjects will also be instructed to discard all used/empty packets but to bring back any unopened packets to the next visit for compliance assessment during both the Run-in and Blinded Treatment Phases. Subjects will be instructed to return the unopened (unused) patiromer/placebo packets in the outer packaging (boxes) in which they were originally provided. The Investigational Pharmacist or the qualified designee as assigned by the Principal Investigator will assess compliance based on returned unopened packets during the entire study to confirm that the subject is taking patiromer/placebo according to the protocol instructions.

Compliance will be documented and assessed on the basis of the prescribed number of patiromer/placebo packets, the duration of treatment, and the quantity of dispensed and returned unused packets. The Investigational Pharmacist or the qualified designee as assigned by the Principal Investigator will inform the study personnel if any compliance issues (e.g., <80% of expected usage) are identified so that the subject can be retrained on proper dosing and administration.

6.6 Site Supply, Storage, Accountability

6.6.1 Site Supply

Once a site has been approved to receive study drug, the site will be supplied with an initial shipment of patiromer/placebo sufficient for 1 to 2 subjects. The need for drug resupply will be assessed on a regular basis taking into account the number of subjects enrolled, the number of subjects in Screening at the site, and the overall enrollment into the study.

6.6.2 Storage

The Investigational Pharmacist or qualified designee as assigned by the Principal Investigator will verify and acknowledge receipt of each shipment of patiromer/placebo. Patiromer/placebo will be shipped and stored under refrigeration (2–8 degrees Celsius); see the Pharmacy Manual for additional details. Upon dispensation to a subject, patiromer/placebo should ideally be kept refrigerated at 2°C to 8°C (36°F to 46°F) if possible, but if stored at ambient room temperature (<25°C (<77°F)) patiromer/placebo must be used within 3 months of being taken out of the refrigerator [24]. All study drugs will be stored in a secure location. No subject other than those enrolled in this specific clinical study are allowed to take patiromer/placebo provided for this study. Patiromer/placebo provided for this study must not be utilized for any laboratory or animal research.

6.6.3 Accountability

All investigational product dispensed to subjects must be accurately recorded on the Investigational Product Accountability Records maintained at the Study Site by the Investigational Pharmacist or the qualified designee as assigned by the Principal Investigator. Subjects will be instructed to return all containers of investigational product dispensed to them (including unused packets and all containers) at each scheduled visit. All used containers will be retained at the site by the Investigational Pharmacist/qualified designee as assigned by the Principal Investigator for the Study Monitor's verification. Investigational product accountability and compliance for all investigational products will be performed by the Investigational Pharmacist or the qualified designee as assigned by the Principal Investigator at each scheduled study visit.

